**Protocol**

**09/16/09**

**Background**

VT is the next frontier in electrophysiology. An increasing number of patients require VT ablation despite optimal medical therapy. Myocardial scars are present in the majority of patients with ischemic and nonischemic cardiomyopathy and usually act as the substrate for reentrant VT. According to pathological findings, rather than being homogeneous tissue, cardiac scars often contain many “channels” of surviving myocardium within the area, which enable electricity to enter, traverse, and exit the scar via different connections within this network and form a “reentry loop” maintaining reentrant VT. Cauterizing the myocardial channels along the scar border in order to interrupt those loops and clinical VT, therefore, is the aim for most reentrant VT ablations. Because of hemodynamic intolerance as well as the pre-existing alternative channels and exit sites, an approach targeting single VT channels identified by their electrical characteristics will not be applicable for the majority of patients. A “substrate-guided” ablation approach is frequently conducted to treat such arrhythmias and involves the placement of linear ablation lesions along the scar

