**Voltage Map Dataset**

All voltage maps will be created by an electrophysiologist using a Carto 3D mapping system and a 3.5-mm Navistar cooled-tip catheter. Bipolar electrograms will be filtered at 10–30 to 400–500 Hz. Standard clinical voltage criteria will be used to define scar (<0.5 mV), abnormal (0.5–1.5 mV), and normal (>1.5 mV) myocardium. Each voltage map will be divided into 17 segments according to the AHA LV model to conduct visual analysis as well as quantitative analysis.

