**HP00043324**  
**NCT01250912**

### **123I-MIBG Imaging Dataset**

For the planar images a whole-heart region of interest (ROI) will be drawn manually to include both ventricles. A square mediastinal ROI (7x7 pixels) will be drawn in the upper mediastinum, using the apices of the lungs as anatomic landmarks. The H/M ratio will be calculated as the ratio of the counts per pixel in the two ROIs. H/M data will be used to calculate myocardial washout using two formulas. Uncorrected washout will be calculated as

$$H/M (early) - H/M (late) / H/M (early).$$

Background corrected washout will be calculated as

$$H (early) - M (early) - H (late) - M (late) / H (early) - M (early)$$

Single aggregate values for each washout parameter will be determined as described above.

For the SPECT image sets, segmental myocardial activity will be scored using a 17-segment model. Each segment will be scored using the following scale: 0 normal tracer uptake, 1 mildly reduced uptake, 2 moderately reduced uptake, 3 severely reduced uptake, 4 absent tracer uptake, NA not assessable. Accordingly, the summed score (SS) for each study could range from 0 to 68 (17x4).

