**Research Part of the Protocol**

Four specific aims were plan to achieved for this research. Specific Aim 1: Evaluate if areas of left ventricular (LV) denervation measured by cardiac 123I-metaiodobenzylguanidine (MIBG) SPECT imaging (innervation map) can be integrated into the CartoXP electrophysiology mapping system. Specific Aim 2: Evaluate, in a group of 20 patients, if areas of denervation in the 3D maps reconstructed from MIBG SPECT imaging correlate with the voltage-map defined scar targeted during VT ablations Specific Aim 3: Determine the changes of cardiac innervation before and 6 months after the VT ablation in 20 patients. Specific Aim 4: Investigate the possible predicting factors for VT reoccurrence within six month after the ablation.

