**HP00043324**  
**NCT01250912**

Differences in scar size, morphology and severity between 3D MIBG innervation maps and EP voltage maps will be analyzed using Student T-test. Segments where diastolic potentials, fractionated potentials and successful ablation sites are located will be investigated in order to identify the characteristics of the MIBG imaging in those segments, e.g. heterogeneity, etc. Segmental/regional washout rate, normalized MIBG activities as well as SS scores will be compared with segmental/regional voltage values in order to identify the relationship between cardiac denervation areas and abnormal endocardial voltage areas.

Differences in size, morphology and severity, regional/global washout from planar images, normalized regional intensities, regional activity summed scores between pre and post ablation 3D MIBG innervation maps will be analyzed using Paired T-test. Global wash out rate will be correlated with HRV indexes before and after the ablation to investigate the relationship between them. Normalized regional MIBG intensities, regional wash out rate and regional SS score both before and after ablations will be compared between VT exit sites segments and other segments with independent sample T-test in order to identify the innervation characteristics of the exit site segments.

Measurements and results will be reported as mean  $\pm$  standard deviation if a normal distribution can be assumed. P values at a level of  $<0.05$  will be considered as statistically significant. Pearson correlation will be conducted to investigate the relationship between two sets of images. The logistic regression will be conducted to investigate the relationship between 3D innervation morphologies, HRV parameters, patient characteristics, clinical VT characteristics and the VT recurrence within the six month

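### The exit-site comparison ignores segmental voltage, so a significant difference may only restate that MIBG uptake follows scar

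*Combined protocol and SAP*

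**What the plan says.** The Data Analysis section plans that three regional MIBG measures (normalised intensity, washout and summed score), before and after ablation, "will be compared between VT exit sites segments and other segments with independent sample T-test". The stated aim is "in order to identify the innervation characteristics of the exit site segments", and P values below 0.05 "will be considered as statistically significant". The other segments are not limited to scar or border zone, and voltage does not enter the test.

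Three other places bear on this:

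- The Background describes surviving channels in scar, "which enable electricity to enter, traverse, and exit the scar via different connections within this network", and gives the usual aim of ablation as "Cauterizing the myocardial channels along the scar border in order to interrupt those loops".
- Specific Aim 2 is to "Evaluate, in a group of 20 patients, if areas of denervation in the 3D maps" correlate with scar as defined by the voltage map.
- The Voltage Map Dataset section sets three classes (scar below 0.5 mV, abnormal 0.5 to 1.5 mV, normal above 1.5 mV) and states: "Each voltage map will be divided into 17 segments according to the AHA LV model". The MIBG section uses the same number of segments: "segmental myocardial activity will be scored using a 17-segment model".

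The Data Analysis section also compares segmental MIBG with segmental voltage, but as a separate analysis that does not feed the exit-site test.

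**The concern.** Two expectations in the protocol combine badly here. Exit sites should lie in or beside scar, and MIBG uptake should be lower in scar. If both hold, the exit-site segment will tend to differ from the average of the remaining segments even when MIBG carries no information about exit sites beyond voltage. The test cannot tell an exit-site characteristic from the general relation between denervation and scar. A significant result could then be reported as an innervation feature of exit sites when it only repeats the finding sought under Aim 2.

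This is separate from the clustering of segments within patients. Analysing each patient's exit segment minus the mean of all that patient's other segments respects clustering, yet it still rejected in 37% to 99% of simulated studies with 30% of segments low-voltage and no exit-site effect. Pairing alone does not cure the problem.

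**Working it through.** The plan states no effect size, standard deviation or power for this test, so there is no figure to reproduce. The question is how often the planned test is significant when there is no exit-site effect beyond voltage.

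**Inputs from the documents:** 20 patients, 17 segments each (20 × 17 = 340 segments), significance level 0.05.

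**Assumed, because the documents are silent:** a two-sided test, one exit segment per patient (20 exit against 320 other segments), the extent of scar, the strength of the MIBG-voltage relation, and where exit sites lie relative to scar.

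**Check 1: scar present or absent.** Let k of the 17 segments be abnormal, let MIBG differ by d standard deviations between abnormal and normal segments, and let every exit site lie in an abnormal segment. Of the 16 other segments, 17 − k are normal, so the expected difference with no exit-site effect is

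d × (17 − k) / 16.

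For k = 6 and d = 1 this is 11/16 = 0.69 SD. The standard error is √(1/20 + 1/320) = 0.23, the ratio is 0.6875/0.2305 = 2.98, and the chance of significance is about Φ(2.98 − 1.96) = Φ(1.02) = 85%. Simulation with a within-patient correlation of 0.3 (3,000 runs) gave 84%. Other settings:

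| Abnormal segments (k) | Normal share of the other 16 | d = 0.5 | d = 1 | d = 1.5 |
|---|---|---|---|---|
| 4 | 81% | 39% | 96% | 100% |
| 6 | 69% | 27% | 84% | 99% |
| 8 | 56% | 18% | 62% | 93% |
| 12 | 31% | 6% | 18% | 35% |
| 15 | 12% | 2% | 4% | 5% |

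At d = 0 the rate is about 2%, so the excess comes from scar. With k = 6 and only 60% of exit sites in scar, the rates fall to 6%, 15% and 26%.

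**Check 2: graded voltage.** Segmental voltage V is standard normal, MIBG = rV + √(1 − r²)e, and the lowest 30% or 50% of segments count as low-voltage. MIBG again depends on voltage only. Each cell gives the percentage of studies significant at r = 0.3 / 0.5 / 0.7. The restricted test compares the exit segment with the same patient's other low-voltage segments.

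| Exit-site position | Low-voltage share | Planned test | Restricted, paired test |
|---|---|---|---|
| Anywhere in low-voltage segments | 30% | 33 / 75 / 98 | about 4 to 6 |
| Anywhere in low-voltage segments | 50% | 20 / 45 / 76 | about 4 to 6 |
| Upper (border) half of low-voltage segments | 30% | 17 / 47 / 83 | 7 / 12 / 27 |
| Upper (border) half of low-voltage segments | 50% | 7 / 11 / 16 | 10 / 20 / 45 |
| Four segments straddling the cut-off | 30% | 11 / 22 / 37 | 11 / 25 / 65 |
| Four segments straddling the cut-off | 50% | 4 / 3 / 1 | 18 / 44 / 82 |

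Repeat runs moved these by a few points. A within-patient model with segmental voltage as a covariate rejected in 4% to 6% of studies in every scenario run.

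**The case against.** The strongest case against has four parts.

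- **Position of exit sites.** The Background places ablation targets along the scar border, not throughout the scar. With border placement the excess is much smaller, and with half the segments low-voltage the planned test rejects in only 1% to 16% of studies. This stands, and it is why the size must be given as a wide range.
- **Stronger readings.** A reader might infer that most other segments are healthy, or that the test is bound to report an exit-site feature. The documents support neither. They give no scar extent, the inclusion criteria do not require scar, and the Background says only that most cardiomyopathy patients have it. The rates also fall close to nominal when scar is extensive, and fall well below those in the first check when many exit sites lie outside scar.
- **The obvious remedy.** Restricting the comparator to segments at or below 1.5 mV looks natural but can mislead. If exit sites lie at the border, the remaining low-voltage segments are denser scar, and exit sites look better innervated for that reason alone. This stands.
- **Descriptive purpose.** The comparison is one of several exploratory ones in 20 patients, no voltage-independent claim is made, and the MIBG-voltage relation will be reported alongside. This lowers the stakes but does not answer the point: the plan attaches a significance test and an identifying purpose to the comparison, and the separate analysis does not adjust it.

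**Conclusion.** The concern holds in a limited form. As planned, the exit-site test cannot separate a characteristic of exit sites from the MIBG-scar relation, and nothing else in the documents separates them.

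How often this would mislead cannot be fixed from the documents. With MIBG depending on voltage only, r from 0.3 to 0.7, and 30% or 50% of segments low-voltage, the planned test gives a false exit-site difference in about 20% to 98% of studies if exit sites fall anywhere in low-voltage segments. The range is about 1% to 84% if they lie at the border. These figures rest on one exit segment per patient, a linear MIBG-voltage relation, and the assumed scar extents and border definitions.

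**What to change.** In the Data Analysis section, replace the independent-sample t-test for exit sites with a segment-level mixed model for each MIBG measure. Exit-site status and segmental voltage are fixed effects, and patient is a random effect. Voltage should preferably be continuous. The three voltage classes are the minimum, and they are weaker because voltage still varies within a class. Base any stated exit-site characteristic on the voltage-adjusted exit-site coefficient. Keep exit against all other segments as a descriptive figure only, and do not rely on the pooled comparator of 1.5 mV or below alone.

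No new data are needed, since voltage is already mapped on the 17 segments. The cost is a little more analysis work, some loss of precision for the exit-site effect, and an assumed form for the MIBG-voltage relation, which should be stated and checked. No repeat voltage map at 6 months is described, so the post-ablation models would adjust for voltage at the procedure. Their exit-site coefficient would also carry any effect of the ablation, and the report should say so.

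### The exit-site comparison pools segments over patients and has no rule for hearts without a localised exit, so patient differences can mimic or mask an exit effect

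*Combined protocol and SAP*

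**What the plan says.** All references are to the combined protocol and SAP.

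- **Data Analysis.** Regional MIBG intensity, washout and summed score, before and after ablation, are "compared between VT exit sites segments and other segments" by an independent-sample t-test. The stated purpose is to characterise innervation at exit sites. P values below 0.05 "will be considered as statistically significant".
- **Voltage Map Dataset.** "Each voltage map will be divided into 17 segments according to the AHA LV model". The SPECT images are scored on 17 segments too.
- **Research Part of the Protocol.** Aim 2 reads "Evaluate, in a group of 20 patients"; Aim 3 also names 20 patients.
- **Background.** "Because of hemodynamic intolerance as well as the pre-existing alternative channels and exit sites", the protocol says, "an approach targeting single VT channels identified by their electrical characteristics will not be applicable for the majority of patients".
- **123I-MIBG Imaging Dataset.** The uptake scale ends with "4 absent tracer uptake, NA not assessable". Exit-site status has no such category.

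The plan does not define how an exit site is identified, how many a patient may have, or what happens to a patient in whom none is found. The inclusion criteria require neither a tolerated VT nor a localised exit. Voltage mapping is the only mapping method described, and the VT characteristics to be collected do not include exit location.

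**The concern.** The test treats exit segments and comparator segments as two unrelated samples, although every heart with a labelled exit contributes to both. A heart with no labelled exit can contribute only to the comparator. The exit group therefore comes from localised patients alone, while the comparator may mix localised and unlocalised patients.

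The Background gives reasons why some patients may have no located exit. If those patients differ in overall innervation, for whatever reason, the difference enters the exit-site contrast. It could create an effect or cancel one. Separately, their true but unlabelled exit segments sit among the comparator segments and shrink any real difference.

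The silence also leaves the handling of these patients to be decided after the data have been seen.

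**Working it through.** The plan gives no effect size, standard deviation or sample-size calculation for this comparison, so there is no figure to reproduce. What follows shows the mechanism and its possible size.

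**Inputs from the document:** 20 patients and 17 segments, so 20 × 17 = 340 segments.

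**Assumptions, not in the document:**
- Each patient has 2 true exit segments.
- u patients have no localised exit, and all their segments are counted in the comparator. In the remaining patients both exits are found.
- g is the difference in mean segment score between localised and unlocalised patients (localised minus unlocalised), unrelated to exit sites. It is taken as 0, 0.25 or 0.5 points.

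**Step 1, group sizes.** Exit segments = 2(20 − u). Comparator segments = 15(20 − u) + 17u.

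**Step 2, composition of the comparator.** Share from unlocalised patients: s = 17u / comparator. Share that are unrecognised exits: c = 2u / comparator.

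**Step 3, what the pooled difference estimates.** Let δ be the true exit effect, and a and b the mean scores of non-exit segments in localised and unlocalised patients, so g = a − b. Then

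(a + δ) − [(1 − s)a + s·b + c·δ] = δ(1 − c) + s·g.

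| u | Exit | Comparator | s | c | s·g for g = 0 / 0.25 / 0.5 |
|---|---|---|---|---|---|
| 0 | 40 | 300 | 0% | 0% | 0 / 0 / 0 |
| 4 | 32 | 308 | 68/308 = 22% | 8/308 = 2.6% | 0 / 0.06 / 0.11 |
| 11 | 18 | 322 | 187/322 = 58% | 22/322 = 6.8% | 0 / 0.15 / 0.29 |
| 14 | 12 | 328 | 238/328 = 73% | 28/328 = 8.5% | 0 / 0.18 / 0.36 |
| 16 | 8 | 332 | 272/332 = 82% | 32/332 = 9.6% | 0 / 0.20 / 0.41 |

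A negative g reverses the sign of the last column. With u from 10 to 18, dilution c is 3.0% to 5.3% for one exit per patient, 6.3% to 10.7% for two and 9.7% to 16.2% for three.

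**Step 4, the within-heart contrast.** For a localised patient i with mean non-exit score a_i, exit mean minus comparator mean = (a_i + δ) − a_i = δ. The patient's own level cancels, and unlocalised patients supply no contrast. What remains is any exit missed in a localised heart: with two true exits and one found, 1 of 16 comparator segments is misclassified, a dilution of 1/16 = 6.25% in that patient.

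**Step 5, power.** Nominal power of the pooled test (two-sided 0.05, effect 0.8 SD, two exits per patient, allowing for dilution but not for g) is 86.8%, 70.2% and 52.4% for u = 11, 14 and 16. Excluding unlocalised patients gives 89.0%, 74.0% and 56.6%. With every patient localised it is 99.7%. These figures treat segments as independent, as the plan does, and are therefore optimistic. They show that the scarcity of labelled exits costs much more power than dilution does.

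**The case against.** A reader might infer that the protocol declares exit sites unmappable in most patients. It does not. The Background sentence concerns an ablation approach, and one of its two reasons is that alternative channels and exit sites exist, which can make targeting one channel insufficient even when that channel is found. Exits might be located by other means. The counts of 11, 14 and 16 unlocalised patients therefore have no basis in the document.

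A reader might also infer that the plan counts unlocalised patients' segments as comparator segments. That is the literal reading of a two-way split, but the plan is silent, and an analyst could equally leave those patients out.

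No passage gives a difference in MIBG score between localised and unlocalised patients, or its direction; at g = 0 there is no such bias. Dilution alone is modest. Exit sites are not named in any of the four aims, so this is a supporting analysis in a small study.

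Finally, it can be said that this is only the familiar fault of an independent test on clustered segments. That is partly right: a within-patient analysis removes the between-patient bias. A correction that only adjusts the standard errors does not, because the bias is in the estimated difference itself.

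All of these limits stand. They do not make the stated test suitable: it is explicitly unpaired and sets no condition for a patient's entry.

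**Conclusion.** The point holds in a limited form. The plan prescribes a pooled independent-sample test for segments from the same hearts, with no definition of an exit site and no rule for patients without one. If such patients enter, the comparison estimates δ(1 − c) + s·g instead of δ.

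The main risk is the term s·g. It may be zero and may have either sign. Its multiplier s would be 22% with 4 unlocalised patients and 58% to 82% with 11 to 16. The dilution c is about 7% to 10% in the latter range. All of this assumes two exits per patient and literal counting of unlocalised patients in the comparator. The document supports the possibility that some patients are unlocalised; it does not support any particular number.

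The change is worth making because the better analysis is cheap and does not depend on these assumptions to remove the between-patient bias.

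**What to change.** In Data Analysis, replace the independent-sample t-test for exit sites with a within-heart comparison, restricted to patients with at least one localised exit site. Either take each patient's mean over exit segments minus the mean over that patient's remaining segments and test it across patients, or fit a segment-level model with patient fixed effects.

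Also:
- state what evidence counts as localising an exit;
- code exit status as unknown where a VT was not localised;
- report how many patients contribute;
- limit the conclusion to localisable VT.

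The cost is a rewritten analysis sentence, an entry condition and one code in the segment dataset. Clinical procedure does not change. No labelled exit segment is lost, since unlocalised patients have none. However, the comparison would rest on 9, 6 or 4 patients if 11, 14 or 16 of 20 were unlocalised, and its scope narrows. The change does not cure a shortage of localised exits, or exits missed in localised hearts; it makes the shortage visible, where the pooled segment count hides it.

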### **Heart Rate Variability**

All the patients will undergo 24-hour ambulatory electrocardiographic monitoring on entrance into the study in order to investigate the prognostic value of heart rate variability (HRV). Time and frequency domain HRV parameters will be calculated from those recordings. Traditional measurements of HRV will be analyzed according to the Task Force of the European Society of Cardiology and the North American society of Pacing and Electrophysiology. Time domain analysis of HRV will include the mean duration of

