**HP00043324**  
**NCT01250912**

all normal-to-normal (NN) intervals (mean RR), standard deviation of all normal-to-normal intervals (SDNN), standard deviation of the averages of NN intervals in all 5-min segments, mean of SDNN in all 5-min segments (SDNN index), square root of the mean of the sum of the squares of differences between adjacent NN intervals, number of NN intervals differing by more than 50 ms from the adjacent interval divided by the total number of NN intervals, and HRV triangular index. HRV parameters will be reacquired 6 months after the ablation.

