**Patient Characteristics**

Patient clinical characteristics (gender, age, ejection fraction, comorbidities, anti-arrhythmia medications) and their clinical VT characteristics (morphology, frequency, duration, cycle length, termination strategy, previous ICD shocks) will be collected.

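### The Aim 4 recurrence regression has at least 19 candidate predictors and no rule for using them; at 20 patients its result could be inestimable or due to chance

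*Combined protocol and SAP*

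**What the plan says.** Aim 4 (Research Part of the Protocol) is to "Investigate the possible predicting factors for VT reoccurrence within six month after the ablation". No number of patients is attached to it. Twenty is stated for Aim 2 and for Aim 3 ("Determine the changes of cardiac innervation before and 6 months after the VT ablation in 20 patients"), and no other patient number appears.

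The analysis is one sentence in Data Analysis: "The logistic regression will be conducted to investigate the relationship between 3D innervation morphologies, HRV parameters, patient characteristics, clinical VT characteristics" and recurrence over the six-month follow-up. The groups are filled in elsewhere:

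- Heart Rate Variability: seven time-domain indices are listed, and "Time and frequency domain HRV parameters will be calculated from those recordings", so frequency-domain measures come on top.
- Patient Characteristics, patient items: "gender, age, ejection fraction, comorbidities, anti-arrhythmia medications".
- Patient Characteristics, VT items: "morphology, frequency, duration, cycle length, termination strategy, previous ICD shocks".
- Innervation morphologies: named in the plural, not itemised.

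The only decision rule is the general one in Data Analysis, significance at P<0.05. No limit on the number of predictors, selection method, penalised or exact fitting, or multiplicity rule is given. HRV is measured at entry and again later ("HRV parameters will be reacquired 6 months after the ablation"); MIBG imaging is also repeated at six months. The regression sentence does not say which values enter.

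**The concern.** The sentence can be carried out in at least four ways: one joint model, a small model selected from the data, single-predictor tests, or a small model chosen in advance. With few patients these do not give interchangeable answers. A joint model can fail outright. A data-selected model capitalises on chance. Single tests at 0.05 can be expected to throw up findings when nothing is predictive. Only the model chosen in advance is safe from these faults, and it would still be imprecise. Because the choice is left until the data are in hand, a reader of the results could not tell a predictor from a chance association.

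A secondary point is timing. The repeat MIBG and HRV values are taken as the recurrence window closes, so they cannot predict what happened within it. The plan should say that Aim 4 uses pre-ablation values.

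**Working it through.** **The plan's own figure.** Twenty cannot be reproduced: no power, effect size, standard deviation or expected number of recurrences is given.

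**Candidates.** Time-domain HRV 7 (mean RR, SDNN, SD of the 5-minute means, SDNN index, root mean square of successive differences, proportion of differences above 50 ms, triangular index) + patient characteristics 5 + VT characteristics 6 = 18 itemised; + at least 1 innervation measure = 19. This is a floor: frequency-domain HRV is omitted, comorbidities and medications count once each, and categorical items get no extra terms.

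**Events per candidate.** Assume n = 20. The rarer outcome has at most 20/2 = 10 patients, so at most 10/19 = 0.53 per candidate, whatever the recurrence rate.

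**Event scenarios.** The documents give no six-month recurrence rate. Two assumed cases are used. The first is 9 events: Background cites 53% long-term success, and 20 × 0.47 = 9.4. The second is a low case of 5 events.

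**Reading 1: joint model.** An intercept plus 19 predictors makes 20 coefficients for 20 patients. If the columns are linearly independent, the outcomes are separated perfectly; if not, the coefficients are not identified. Either way there is no usable maximum-likelihood fit. Simulation with independent normal noise predictors, using a linear-programming test for complete separation, gave:

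| n | Predictors | Separation across event scenarios |
|---|---|---|
| 20 | 19 | 100% |
| 20 | 12 | about 90–99% |
| 20 | 5 | about 2% (9 events), 10% (5 events) |
| 20 | 1–3 | under 1% |
| 30 | 19 | about 96–100% |
| 40 | 19 | about 40–86% |
| 60 | 19 | no more than about 9% |

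**Reading 2: one test per candidate at 0.05, nothing predictive.** Expected false positives:

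- Every test of size exactly 5%: 19 × 0.05 = 0.95. If the tests were also independent, the chance of at least one is 1 − 0.95^19 = 62%.
- Exact tests with 6 of the 19 binary: Fisher's test at this size rejects only about 1.3–2.8% of the time. Then 13 × 0.05 + 6 × 0.013 = 0.73, and 13 × 0.05 + 6 × 0.028 = 0.82. More binary candidates would lower it further.
- Likelihood-ratio tests (simulated, HRV indices correlated at 0.8, 6 candidates binary): about 1.2 (9 events) and 1.4 (5 events).
- Wald tests, same simulation: about 0.6 and 0.2.

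**A single predictor named in advance.** From simulated Firth fits with no true effect, the median standard error per SD of the predictor is 0.474 (9 events) and 0.529 (5 events). exp(1.96 × 0.474) = 2.5 and exp(1.96 × 0.529) = 2.8, so the 95% interval for the odds ratio runs about 2.5- to 2.8-fold either side of the estimate. With a true difference of 1.33 SD it widens to about 4-fold. By two-sided t-test, 80% power needs a difference of about 1.33 SD (9 v 11 patients) or 1.53 SD (5 v 15). Power at 0.8 SD is 39% and 31%.

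**The case against.** The best defence is that Aim 4 is the last aim of a small imaging-integration study, is worded as a search for possible factors, and has no stated decision resting on it. That stands, and it lowers the severity. It does not supply the missing rules: P<0.05 applies throughout Data Analysis, and nothing tells a reader to treat a significant Aim 4 result as hypothesis-generating.

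Several stronger readings are tempting, and the documents do not support them:

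- *All 19 candidates will enter one model.* The sentence names groups. It does not say that every collected item enters together, so the 100% separation figure describes one permitted reading and is not a prediction of what will be done.
- *Aim 4 has 20 patients.* That is inferred from Aims 2 and 3. With 60 patients a 19-predictor model would usually be estimable, though still with few events per predictor.
- *About one false positive must be expected.* That depends on the test: the count is lower with exact tests on binary candidates and much lower with Wald tests.
- *The plan will report an over-optimistic ROC curve for recurrence.* The ROC sentence concerns innervation against the voltage map.
- *Six-month values will be used as predictors.* Heart Rate Variability ties prognostic use to the recording at study entry, and Measures to Reduce Risks puts imaging before mapping. Baseline is the natural reading, so timing needs only a clarifying sentence.

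It can also be said that restricting the model to one or two predictors narrows the aim. That is true of the model, but the other candidates would still be reported.

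**Conclusion.** The point holds at moderate severity. The plan names an ordinary logistic regression on at least 19 candidates, with a significance threshold and nothing else to govern it. Under the assumption of 20 patients, a joint model of all candidates cannot be estimated and one of 12 would nearly always separate on noise. Single tests would give roughly 0.2 to 1.4 false positives depending on the test. The limit of 0.53 patients per candidate needs only n = 20. The simulated figures also rest on 9 or 5 events and on the stated noise structure; the separation figures use independent continuous predictors. A small model chosen in advance avoids separation, but the current text neither requires nor describes one. The documents support a finding that the analysis is left open at a size where the choice decides the result. They do not show that a failing analysis has been chosen.

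**What to change.** In Data Analysis:

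1. State that Aim 4 is exploratory, give its number of patients, and specify pre-ablation MIBG and HRV values as predictors.
2. Replace the open regression with a model of at most one or two predictors, named in advance by the investigators. Fit it by Firth or exact logistic regression and report odds ratios with profile-likelihood or exact 95% intervals.
3. Report the remaining candidates one at a time with intervals and without significance claims.
4. State that neither an unpenalised joint model nor a data-selected model will be interpreted as identifying predictors.

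The cost is some wording and one advance choice; no further data or patients are needed. Aim 4 would claim less and would remain imprecise and low powered, as the interval widths and detectable differences above show. The change makes the result interpretable; it does not make Aim 4 well powered.
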